8.5.2.2 Adverse events secondary to other adverse events

In general, AEs secondary to other AEs (cascading events or sequelae) should be identified according to the primary cause, with the exception of serious events. A medically important AE secondary to an AE that is separated in time from the initial event should be reported as a separate event in the EA section of the eCRF. For example:

If vomiting results in mild dehydration without additional treatment in a normal adult, vomiting should only be reported on the eCRF.

If vomiting results in severe dehydration, both events should be reported separately on the eCRF.

If severe gastrointestinal bleeding leads to renal failure, both events should be reported separately on the eCRF.

If a dizziness event leads to a fall and subsequent fracture, then all three events should be reported separately in the eCRF.

If neutropenia is accompanied by infection, both events should be captured independently in the eCRF.

All EAs must register separately if there are concerns regarding the association of events.

8.5.2.3 Persistent or recurrent adverse events

A persistent adverse event is one that spreads continuously without resolution between different patient assessment points. Such events only need to be registered once in the eCRF. The initial severity (intensity or degree) of the event will be recorded at the time of the first AD record. If a persistent AE becomes acute, the maximum severity should be recorded in the appropriate section of the eCRF. If the event becomes a serious event, it must be reported no later than 24 hours after the knowledge of the change in the status of the event. The eCRF section should be updated to reflect serious status and will record the date on which the event became serious, thus completing all relevant serious EA reporting data.

A recurrent AE is one that resolves between assessment points and subsequently reappears. Each recurrence of the EA must be recorded separately in the eCRF.

8.5.2.4 Abnormal vital signs

Not all abnormal vital signs qualify as AE. For an abnormal vital sign to be reported as an AD, it must meet any of the following criteria:

Be accompanied by clinical symptoms. It results in a change in treatment (dose modification, treatment interruption, etc.).

The report on abnormal values should focus on obtaining a diagnosis and not just a description of the abnormality.

8.5.2.5 Death

Death should be considered an outcome and not an event. The event or condition that caused or contributed to the fatal outcome should be recorded as the EA in the eCRF section.

8.5.2.6 Pre-existing medical conditions

A pre-existing medical condition should be recorded as AE only if the frequency, severity, or characteristics of the condition worsen during the study.

8.5.2.7 Hospitalization or prolonged hospitalization

Any AE that results in hospitalization or prolongation of hospitalization must be documented or reported as a serious AE with the following exceptions:

Hospitalization for pre-existing conditions if the following are met:

Hospitalization was planned before the study.

8.5.2.8 Pregnancies, miscarriages, and birth defects

Fertile women should contact their doctor to report any suspected pregnancy during the study. A pregnancy report must be issued, and the sponsor must be informed immediately.

Monitoring of the patient should continue until the outcome of the pregnancy. Pregnancy is not in itself an AE.

Any abortion should be classified as a serious AE.

Any birth defect or birth defect in a product from a woman who received the study drug should be classified as a serious AE.

8.5.3 Procedures for a serious adverse event

The process of attention to the adverse event considers the following stages:

[figure not shown]

Figure 3. Adverse Event Care

During the development and conduct of this study, undesirable harmful events or adverse reactions/incidents, of medical implication, may occur in the research subject, which do not necessarily have a causal relationship with the investigational products. These harmful phenomena can occur during the use of investigational pharmaceutical products at doses authorized for use in humans by a local, national or international regulatory entity. However, it may be suspected that the

investigational product causes some unwanted clinical manifestation. AEs, Incidents, Adverse Incidents, ADRs or SRAMs to one or more pharmaceutical products can occur during the systematic evaluation of the participants (on the days when the clinical review is scheduled, according to the schedule of activities) or suddenly, in such a way that:

1. The investigator must be the first person to whom the subject notifies that he or she has developed or presented any harmful phenomenon of a clinical nature during his or her participation in this study.
2. According to his clinical judgment, Based on the pertinent physical examination, interrogation, etc., as well as the analysis of the information available in the medical literature and what is referred to in the Investigator's Manual, Information to prescribe or Summary of the Comparator Drug Label, the principal investigator determines the pertinent care of the harmful event/reaction.
3. Such care can be in the research center or in the hospital with the greatest resolution power. In such a way that, if the subject is sent by the PI to a hospital, he or she attends through a referral system. The reference can be with a card that identifies the subject as a study participant and links him or her to the pre-established agreement with the institution, or through a medical reference note issued by the Principal Investigator. Laboratorios Sophia, S.A. de C.V., will pay the expenses for the medical care of the participating subject, when the adverse event is associated with or is related to the product under investigation.
4. Taking the clinical information collected, either during the care provided at the research center or that provided by the treating physician(s) in the hospital, the PI will record the AE in its clinical note, stating the seriousness, intensity (mild, moderate or severe) and relationship with the investigational product.
5. The PI must migrate the relevant data to the eCRF and its respective adverse event section. By, in cases of serious adverse events, the clinical monitor of the study must be notified within 24 hours after learning it, so that in turn it informs the Clinical Team and the UTFLS, and that the CEI/CI is subsequently notified. Non-serious adverse events will be recorded and treated appropriately, and the safety profile of the investigational drug or PI will be reported to the appropriate regulatory entity in the final report of the clinical trial.

The recording of the outcome of the AE depends substantially on the follow-up that the Principal Investigator performs on the subject, since it is expected that most of the harmful phenomena (see subsection 2.5 Risk-benefit assessment and consult the Investigator's Manual) are ophthalmic in nature, however, there may be systemic alterations. Therefore, in the opinion of the researcher, the withdrawal of the participant or their permanence will be considered.

8.5.4 Causation assessment

Causality assessment is the methodology used to estimate the probability of attributing the observed adverse event to a pharmaceutical product. It considers probabilistic categories according to the available evidence and the quality of the information, based on the national pharmacovigilance and technovigilance regulations. [36][50]

An adverse event may or may not be related to the clinical trial. A causal relationship means that the intervention caused (or is reasonably likely to have caused) the adverse event. This usually implies a relationship between the time of the intervention and the adverse event (e.g., the adverse event occurred shortly after the subject under investigation received the intervention). [49]

For all adverse events, the Principal Investigator is responsible for examining and evaluating the patient to determine the association of the event with the clinical study and the intervention, whether it is related to the experimental treatment, concomitant, surgical procedure, or diagnostic procedures performed during the study. [49]

Accepting that the adverse event is related to the clinical study requires a plausible mechanism of action—that is, that there is a logical sequence between the event that occurred and the intervention that caused it. In some cases, it is helpful to know the opinion of other doctors directly or indirectly involved in the research; as well as whether the patient considers that there is a relationship. [49]

The Pharmacovigilance and Technovigilance Unit of Sophia Laboratories (UFTLS) may use the categories of causality described by *the Uppsala Monitoring Centre*, to categorize the likelihood of adverse event to the investigational product or concomitant treatments or treatments used during visits: [36] [50]

- Definitive (certain): a clinical event, including alterations in laboratory tests, that manifests itself with a plausible temporal sequence in relation to the administration of the drug, and that cannot be explained by concurrent disease, or by other drugs or substances. The response to drug withdrawal (withdrawal) must be clinically plausible. The event must be definitive from a pharmacological or phenomenological point of view, using, if necessary, a conclusive re-exposure (challenge) procedure. [36] [50]
- Probable: A clinical event, including alterations in laboratory tests, that manifests itself with a reasonable time sequence in relation to the administration of the drug, that is unlikely to be attributed to concurrent disease, or to other drugs or substances, and that a clinically reasonable response is presented upon withdrawal. It is not necessary to have re-exposure (challenge) information to assign this definition [36] [50]
- Possible: A clinical event, including alterations in laboratory tests, that manifests itself with a reasonable time sequence in relation to the administration of the medicinal product, but which can also be explained by concurrent disease, or by other drugs or substances. Information regarding the withdrawal of the drug may be missing or unclear. [36] [50]

- Unlikely: A clinical event, including alterations in laboratory tests, that manifests itself with an unlikely temporal sequence in relation to the administration of the drug, and that can be more plausibly explained by concurrent disease, or by other drugs or substances. [36] [50]
- Conditional/Unclassified: A clinical event, including alterations in laboratory tests, reported as an adverse reaction, for which further data are essential for appropriate evaluation, or additional data are under review. [36] [50]
- Non-assessable/Unclassifiable: A notification that suggests an adverse reaction but cannot be judged because the information is insufficient or contradictory, and that cannot be verified or completed in its data. [36] [50]

Thus, the degree of certainty to establish the investigational product as the causal agent of the harmful phenomenon that occurs to the subject of the clinical study, can be indicated directly by the Principal Investigator based on his clinical experience or by applying the categories of causality described by *the Uppsala Monitoring Centre*. It is important that the researcher and the UFTLS consider the following arguments in favor of the causal relationship:

- a) Strength of association, which refers to the number of cases in relation to those exposed.
- b) The consistency of the data, i.e. the presence of a common characteristic or pattern.
- c) The exposure-effect pattern, which determines the relationship with the site of appearance, time, dose and reversibility after deletion.
- d) Biological plausibility, which refers to the possible pharmacological or pathophysiological mechanisms involved in the development or presentation of the adverse event.
- e) Experimental findings, e.g., the appearance of abnormal metabolites or high levels of the drug or its biotransformation product.
- f) Analogy, which refers to the experience gained with other related drugs, adverse reactions frequently produced by the same family of pharmacological agents.
- g) Nature and characteristics of the data, i.e. objectivity, accuracy and validity of the relevant documentation. [51]

8.6 Unanticipated Issues

Unanticipated problems (PNA) consider those situations that pose risks to the participating subjects, in general, any incident, experience or result that meets all the following criteria:

- Unexpected in terms of its nature, severity, or frequency in relation to: 1) study-related documents such as investigator's manual, study protocol, and informed consent form; and 2) the characteristics of the population being studied.
- Related or possibly related to your participation in the study (possibly related means that there is a reasonable possibility that the incident, or results, was caused by study procedures).

- Indicative that the research places participants at a higher risk of harm (including physical, psychological, economic, or social) than previously recognized.

8.6.1 Reporting Unanticipated Issues

The PI will be responsible for reporting NAPs to the sponsor, IC and IEC. The report must contain the following information:

- Identification of the study: protocol title and number, name of the PI and, if applicable, of the center.
- Detailed description of the event, incident, experience, or outcome.
- Explanation, justification of the reasons why the incident represents a NAP.
- Description of changes to the protocol or corrective actions taken or proposed in response to the NAP.

NAPs that are SEA must be reported to the IEC/IC and the sponsor within the first 24 hours of the PI becoming aware of it.

Any other NAPs will be reported to the IEC/IC and the sponsor within the first 5 business days after the PI becomes aware of it.

9. Study Monitoring

The study sponsor is responsible for monitoring the study. Monitoring activities include, but are not limited to general safety monitoring, general study quality monitoring, monitoring by study site, detection monitoring, reporting and tracking of adverse events, monitoring for resolution of discrepancies in data capture, etc.

Responsibility for monitoring activities and ultimate responsibility for monitoring rests with the sponsor.

The details of the monitoring activities are specified in a separate document from this protocol in a Monitoring Plan.

9.1 Monitoring the Study Site

The research center participating in the study will be monitored. For each center, at least one start visits and one closing visit must be carried out, which does not exclude the carrying out of one or more follow-up visits between these two mandatory visits.

The initial visit must be carried out before the inclusion of the first participant in that center; In it, the monitor will verify that the material to be used during the study has been received and that the personnel who will participate in the study activities have been trained on the study, as well as verify that the regulatory requirements and applicable standard operating procedures are met.

At the follow-up visit(s), the monitor will conduct a review of the study documents to confirm that the applicable research protocol and standard operating procedures are being followed, data completion is complete and timely, and that adverse event reports are being conducted appropriately. At each visit, the monitor will discuss the findings with the researcher and define the actions to be taken.

The closure visit will take place at the end of the study, once the last site participant has been discharged from follow-up. On this visit the monitor will verify that the site has all the necessary documents for archiving, that all biological samples have been analyzed, that all IP (used and unused) has been returned to the sponsor, and that all unused material has been recovered.

Details on monitoring are set out in the corresponding plan.

9.2 Audit and quality control

To ensure compliance with GCPs and all applicable regulatory requirements, Laboratorios Sophia, S.A. de C.V. may conduct quality assurance audits. Regulatory agencies could also conduct a regulatory inspection of this study.

Details about the audit process are set out separately in the Audit Plan.

9.2.1 Pre-study audit

The research center included in the study will be subject to a feasibility visit prior to the selection of the center, where it will be verified that they meet the minimum requirements indicated by the sponsor.

9.2.2 Audit during the conduct of the study

They may take place at any time before, during, or after the conclusion of the study. If any audit or inspection is conducted, the investigator and the institution shall agree to allow the auditor/inspector direct access to all relevant documents and shall allocate their time and that of their staff to the auditor/inspector to discuss the findings and any pertinent problems. If the audit has not been scheduled by the sponsor, the facility must notify Laboratorios Sophia, S.A. de C.V. immediately.

10. Sample size calculation and statistical analysis

10.1 Sample Size Calculation

The sample size calculation was performed based on the primary objective of the study, to evaluate the safety and tolerability of the PRO-201 ophthalmic solution manufactured by Laboratorios Sophia, S.A. de C.V. on the ocular surface of ophthalmologically and clinically healthy subjects. To meet this objective, it is estimated that 29 subjects will contribute one eye (right eye [OD]) to the study.

10.1.1 Calculation methodology

Atropine sulfate 0.01% has sufficient scientific evidence that confirms its efficacy and safety as an adjuvant in the treatment to delay the progression of myopia in children. In the meta-analysis carried out by Zhao et al (2019), in a sample of 1079 subjects from 7 clinical studies (505 in the 0.01% atropine group and 574 in the control), the incidence of AEs in 0.01% atropine sulfate was statistically lower compared to the control group [OR=0.26, 95% CI (0.11, 0.61)]. While, in the review by Li et al (2019), children who received 0.01% atropine had a better balance between the use of the treatment-incidence of AD, being well tolerated at this concentration (only 2% had photophobia). On the other hand, in the meta-analysis by Wang et al (2020), no study reported severe/serious AEs after administration of 0.01% atropine. Finally, the meta-analysis by Huang et al. (2016), in agreement with these results, mentions that low-dose atropine (0.01%) is one of the most effective interventions with a minimal prevalence of clinical symptoms. Considering this information and the primary objective of the study, the following proposal was made for the sample size. [52, 53, 54, 55, 25] [52] [25][53][54]

For one-arm clinical studies (*single-arm trials*) where the primary endpoint depends on the duration of the study (e.g., survival rate, AD incidence, etc.), there are options available in the literature for sample size calculation. The most common options are the *log-rank* and assuming exponential distribution. Another option for calculation is to use a parametric exact test, following a Chi-square distribution. [56]

The probability that a subject will experience no improvement during the study is given by:

$$d = \int_0^{\infty} G(t) \cdot f_1(t) dt$$

Where $F_1(t)$ is $f(t)$ with $\theta = 0.1$ (θ is a scale parameter, and β is the form of the parameter that determines the shape of the risk function [if $\beta > 1$ the risk increases over time, and if $\beta < 1$ the risk decreases over time, when $\beta = 1$ represents a special case of exponential distribution with constant risk]). Dividing the number of events by d given the sample size adjusted for possible losses. [56]

Considering the OR calculated in the meta-analysis by Zhao et al, and the time of exposure to the product (14 days = 0.47 months) and follow-up time (21 days = 0.7 months), we can expect according to the simulation performed by Phadnis, a rate of 0.09 AE/subject in the study. Considering this incidence rate, in a sample of 24 subjects, 9% could present AE during one month of follow-up, see [52] [56]annex 16.5 Number of events/sample size for the exact method vs. the Wu method, for different values of the parameter β , cumulative time a , and tracking time f

10.1.2 Size Calculation

The PRO-201 ophthalmic solution is expected to be safe in its ophthalmic application when it has an incidence of unexpected, related AEs of less than 10%, and is tolerable when it has an incidence of photophobia that is less than 15% of the study population.

On this basis, a sample of 24 ophthalmologically and clinically healthy subjects was estimated. This value was increased by 20% considering possible losses. Based on this consideration, 29 subjects (who will contribute one eye, OD) are required to respond to the primary objective of the study.

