measures of central tendency: mean, standard deviation, and ranges. Qualitative data will be presented as frequencies and percentages. The statistical analysis to rule out differences will be carried out by means of non-parametric statistics. The Kolmogorov-Smirnov statistic will be used for a sample and the Mann-Whitney statistic (when applicable). The analysis for qualitative variables will be performed by means of Pearson's χ^2 (Chi-square) test or Fisher's Exact test (when applicable). For all analyses, a $p < 0.05$ and an alpha of 0.05 (two-tailed) will be considered significant.

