3.2 Hypothesis

H0= The PRO-201 ophthalmic solution is not safe in its ophthalmic application as it has an incidence of unexpectedly related adverse events (AEs) greater than 10% and is not tolerable as it presents an incidence of photophobia greater than 15% of the study population.

$$H_0: p - p_0 \leq -\delta$$

H1= PRO-201 ophthalmic solution is safe in ophthalmic application with an incidence of unexpected, related adverse events (AEs) of less than 10% and is tolerable with an incidence of photophobia of less than 15% of the study population.

$$H_1: p - p_0 > -\delta$$

4. Study design

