5.2.2 Substitution of subjects

The sponsor, with the prior authorization of the research ethics committees, may decide to replace the subjects who withdraw their FCI or those who present loss of follow-up, until the necessary sample size is completed.

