7.4.4 Definition of variables, methods and scales for their measurement

Board 1. Operational definition of variables

Variable	Conceptual Definition	Operational Definition	Measurement Type	Reference value	Statistical test
Incidence of unexpected-IP-related AEs	Any adverse medical event that occurs in the clinical research subject to whom the PI was administered that has a certain causal relationship with the PI and is not expected. [36]	All AEs (according to the protocol) in which the PI suspects a causal relationship with the PI will be reported.	
 • Discrete quantitative • Nominal qualitative 	< 10%	
 • U for Mann Whitney • Pearson X² or Fisher Exact*
Photophobia incidence	Expected-PI-related AE	Present / Absent	
 • Discrete quantitative • Nominal qualitative 	< 15%	
 • U for Mann Whitney • Pearson X² or Fisher Exact*
Pupillary diameter	The natural pupil of the human eye is usually approximately circular, for a given subject, the pattern of aberrations, diffraction, depth of field and retinal illumination depends on the pupillary diameter, which in turn	The pupillary diameter results from the balance between the pupil sphincter muscle and the radial fibers of the iris that have only autonomic innervation. [37] It will be evaluated through the OPD scan.	Continuous quantitative	2 – 6 mm	Kolmogorov-Smirnov or Mann Whitney U*

Variable	Conceptual Definition	Operational Definition	Measurement Type	Reference value	Statistical test
	varies depending on the ambient lighting.				
Incidence of AD	Any adverse medical event that occurs in the clinical research subject to whom the PI was administered. [36]	All AEs (according to the protocol) will be reported and not just those where the PI suspects a causal relationship with the PI	• Discrete quantitative • Nominal qualitative	• Incidence • Seriousness (severity) • Causality	• U for Mann Whitney • Pearson X ² or Fisher Exact*
Changes in the AVMC	Clinical assessment of near visual acuity allows visual ability to distinguish letters to be assessed.	It will be evaluated by means of the ETDRS booklet for near vision (annex16.1 ETDRS Primer for Near Vision), using the font size in logMAR.	Continuous quantitative	0.1 or better	Kolmogorov-Smirnov or Mann Whitney U*

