10.3.1 Population Analysis

The statistical analysis will be presented to give a general summary of the subjects entered the study and a view of the safety and tolerability of its results. The data provided by the research site will be summarized for this purpose, according to its nature. The Shapiro-Wilk test will be performed to find out if the quantitative data are distributed in a normal way ($p>0.05$).

The results of the quantitative variables will be presented in measures of central tendency: mean, standard deviation, maximum and minimum. Changes in pupillary diameter, near visual acuity, BCVA and OCI will be expressed as continuous variables. Changes in IOP, HR, systemic blood pressure, and TF will be expressed as discrete variables.

The result of the nominal and ordinal qualitative variables will be presented in frequencies, proportions and/or percentages. For these, 2 x 2 frequency tables will be built. All percentages will be presented with decimal.

The level of difference to consider significance will be an alpha (α) of 0.05 or less. The triangulation between the variable type and the measurements is shown in the Board 4 Triangulation of concepts.

Board 4 Triangulation of concepts

Variable Type	Variable	A1	A2	B1	C1	C2	D1	D2	D3	E1	E2	E3	E4	E5
Selection														
A1	Demographic			D										
A2	Medical History/Selection Criteria				D									
Basal														
B1	Comprehensive ophthalmological evaluation			DT	D	TB			TB					
Safety & Tolerability														
C1	Incidence of AE*				TB			TB						
C2	Incidence of photophobia				TB	TB		TB			T			
Secondary Security Outcome														
D1	Pupillary diameter					B	TB							
D2	Incidence of AD				TB	TB		TB						
D3	Near visual acuity			D			TB	B						
Exploratory														
E1	BCAV			D			TB		B					
E2	PIO			D			TB		B					
E3	Corneal and conjunctival stains with fluorescein and lysmine green			D			TB			B				
E4	Vitals signs			D			TB			B				
E5	OCI			D							B			

Abbreviations: BCVA, best corrected visual acuity; B, bivariate analysis; D, descriptive statistics; AE, adverse event; OCI, ocular comfort index; M, multivariate analysis; IOP, intraocular pressure; T, 2x2 contingency table. *Unexpected-related AEs.

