10.3.2 Safety and tolerability analysis

10.3.2.1 Analysis for Primary Variables

An analysis of safety and tolerability outcomes will be carried out in the safety population, defined as any subject who has received at least one dose of the investigational product (PRO-201) regardless of adherence to it or adherence to the protocol (intention-to-treat population, ITT).

The statistical analysis for the primary variables of a quantitative type will be estimated by means of the Kolmogorov-Smirnov statistic for the difference in measurements, once the values have been adjusted with respect to their baseline within everyone. In cases where applicable, the nonparametric Mann-Whitney U test will be used.

For conjunctival hyperemia, Pearson's X² or Fisher's exact test will be used at expected values less than 5.

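### The plan does not support its statement that 29 subjects are required: no test against the 10% or 15% limit is named, 0/29 rejects 10% only one-sided, and the base of 24 cannot be reproduced

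*Combined protocol and SAP*

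**What the plan says.** Section 3.2 and the synopsis set a two-part hypothesis. In words, the safety half is "H1= PRO-201 ophthalmic solution is safe in ophthalmic application with an incidence of unexpected, related adverse events (AEs) of less than 10" per cent, and the tolerability half is photophobia below 15%. In symbols, H1 is p − p0 > −δ, with no value for δ and no definition of p.

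Section 10.1.2 repeats the two limits, says that 24 subjects were estimated on that basis, adds 20% for losses, and concludes that "29 subjects (who will contribute one eye, OD) are required to respond to the primary objective of the study". The synopsis describes the planned 29 as evaluable.

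On the error level, the synopsis says "an alpha of 0.05 (two-tailed) will be considered significant" for all analyses. Section 10.3.1 says "The level of difference to consider significance will be an alpha (α) of 0.05 or less" and gives no side.

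On the test, Board 1 in section 7.4.4 lists "U for Mann Whitney" and Pearson chi-square or Fisher exact for both primary incidences. Section 10.3.1 puts qualitative variables into 2 x 2 tables. In section 10.3.2.1 the sentence on Pearson or Fisher begins "For conjunctival hyperemia", which is not one of the outcomes in section 7.4.

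On the denominator, section 10.3.2.1 analyses "any subject who has received at least one dose of the investigational product (PRO-201) regardless of adherence to it". Under section 5.2.2 the sponsor "may decide to replace the subjects who withdraw their FCI or those who present loss of follow-up".

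**The concern.** The primary conclusion is whether each of two proportions lies below a fixed limit. For that, a single-arm plan needs a one-sample test, a confidence bound or a maximum number of events, and none is given. Mann-Whitney, Fisher and a 2 x 2 table need a second group, and this study has none.

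Two things are at stake. First, whether a completely clean safety result supports the word safe depends on a test and a side that could be chosen after the data are seen. Second, the statement that 29 subjects answer the objective needs a calculation that leads from the limits to the number, and sections 10.1.1 and 10.1.2 do not show one.

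**Working it through.** **Inputs.** Limits 10% and 15% (sections 3.2 and 10.1.2); alpha 0.05 two-tailed (synopsis); base 24 and 20% for losses (10.1.2); 0.09 adverse events per subject and 0.7 months of follow-up (10.1.1); 2% photophobia cited from the literature (10.1.1); annex 16.5.

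**Step 1: the plan's own figure.** 24 × 1.20 = 28.8, rounded up to 29. This step reproduces.

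**Step 2: where 24 comes from.** Section 10.1.1 obtains a sample size by dividing a number of events by d, but states no number of events. Annex 16.5 compares median times of 2.5 and 3.75 months (one-sided 0.05, power 0.80), so neither 10% nor 15% enters it. Its only cell with 24 subjects is the Wu method at a = 12, f = 2. That cell has 19 events in 24 subjects (19/24 = 0.79) and 2 months of follow-up, against 0.09 events per subject and 0.7 months here. No power is stated for 24 or 29. The value 24 does not reproduce.

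**Step 3: the best possible safety result against 10%, two-tailed 0.05.** With 0 events in n:
- Exact lower tail: 0.9^29 = 0.0471; doubled, 0.094.
- One-sample chi-square: n × 0.1/0.9 = 29 × 0.1/0.9 = 3.22; p = 0.073.
- Clopper-Pearson 95% upper limit: 1 − 0.025^(1/29) = 11.9%.

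None of these rejects 10%. By the exact test, zero events first rejects at n = 36 (0.9^35 = 0.02503; 0.9^36 = 0.0225, below 0.025).

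**Step 4: the same result against 15%.** 2 × 0.85^29 = 0.018; chi-square 29 × 0.15/0.85 = 5.12, p = 0.024. This limit is rejected two-tailed.

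**Step 5: one-sided 0.05, exact binomial.**
- Against 10%: 0/29 p = 0.047 (rejects); 0/28 p = 0.9^28 = 0.052; 0/24 p = 0.9^24 = 0.080; 1/29 p = 0.199. The last three do not reject.
- Against 15%: 1/29 p = 0.055 (does not reject); 1/30 p = 0.048 (rejects).

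The rule by number dosed is therefore:
- n = 28: safety cannot be shown.
- n = 29: 0 adverse events and 0 photophobia.
- n = 30: 0 adverse events and at most 1 photophobia.

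**Step 6: chance of meeting both halves, one-sided exact.** Assumptions: 2% photophobia, independence of the two endpoints, and a true unexpected-event rate q of 0.1%, 1%, 2% or 5%.
- n = 29: 0.98^29 × (1 − q)^29 = 54%, 42%, 31%, 13%.
- n = 30: P(at most 1 photophobia) = 0.880, times (1 − q)^30 = 85%, 65%, 48%, 19%.

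**Step 7: if the rule is only that the observed incidence falls below the limit.** At n = 29 this allows at most 2 events (2/29 = 6.9%; 3/29 = 10.3%) and at most 4 photophobia cases (4/29 = 13.8%; 5/29 = 17.2%).
- A true 10% event rate passes its endpoint with P(X ≤ 2) = 43.5%.
- A true 15% photophobia rate passes its endpoint with P(X ≤ 4) = 55.5%.

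**Step 8: direction of the printed hypotheses.** If p is the incidence, p − p0 > −δ is satisfied by large p, which does not match an alternative of less than 10%.

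**The case against.** The strongest reply is that H1 is directional, so a one-sided test is natural. One-sided at 0.05, 29 is the smallest number for which zero events rejects 10%. That is correct and softens the two-tailed result. But the only side set for this trial's analyses is two-tailed; the one-sided level appears only in a table reproduced from the literature. Even one-sided, the margin is a single subject and allows no event.

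Board 1 also places the two limits beside Pearson chi-square, marked as applying where applicable, so a one-sample reading is possible. On that reading 0/29 still gives p = 0.073 two-tailed.

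A small Phase I study in healthy volunteers can reasonably be descriptive, and section 4.2 argues for a small sample. That supports keeping 29. It does not support stating H0 and H1 and calling 29 required.

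A reader might go further and infer that the plan's own method calls for about 176 or 178 subjects, because the annex has a cell of 16/176 = 0.09 and 16/0.09 = 178. The documents do not support that. They never equate d with 0.09, never say that 16 events were used, and the Wu cell 14/151 also rounds to 0.09. What stands is that the derivation is not shown.

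**Conclusion.** The concern holds. The plan makes a pass/fail claim on two proportions without a rule for deciding it, and the sample size is not derived from the limits that it is said to serve. At two-tailed 0.05 by the exact or Pearson one-sample test, no result in 29 subjects can show the event rate to be below 10%. One-sided at 0.05, only 0/29 can, and the result depends on at least 29 being dosed. Replacement is optional and everyone dosed is analysed, so the denominator may fall on either side of 29.

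Three stronger readings should be avoided:
- That 0/29 can never support the safety claim. This is limited to the 10% limit, the two-tailed level and the two tests named. A mid-p test would reject (2 × 0.5 × 0.0471 = 0.047), but the plan does not mention one.
- That a product at the limits passes the observed-incidence rule about half the time. That is per endpoint. With both rates at their limits and independent, the joint figure is 0.435 × 0.555 = 24%.
- That 29 is the wrong number. It is adequate for estimation at the precision given below.

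The chances of success rest on the assumed rates and on independence. The p-values and limits rest only on the stated limits, alpha and number of subjects.

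**What to change.** Keep 29 and settle the following before the data are analysed.

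1. In section 10.1.2, replace the statement that 29 are required, and the annex-based derivation of 24, with the precision delivered. Exact two-sided 95% intervals are 0 to 11.9% for 0/29, 0.1 to 17.8% for 1/29 and 0.8 to 22.8% for 2/29. Reconcile the synopsis's 29 evaluable subjects with 29 as 24 plus losses.
2. In Board 1 and sections 10.3.1 and 10.3.2.1, replace the two-group tests and 2 x 2 tables for the two primary incidences with a Clopper-Pearson interval in the safety population. Correct the conjunctival hyperemia sentence.
3. Then choose one:
   - Remove H0 and H1 from the synopsis and section 3.2, or relabel them as descriptive targets.
   - Keep them, written as p ≥ 0.10 against p < 0.10 and p ≥ 0.15 against p < 0.15. Name an exact one-sample binomial test for each, and state one side consistently in the synopsis and section 10.3.1. Give the rejection rule by number dosed (step 5 if one-sided 0.05) with its chance of success. If two-tailed 0.05 is kept, say that the safety half cannot be shown with 29.

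The cost is protocol and SAP wording. No subjects are added and no study procedure changes. The downside is that the stated claim becomes less favourable.
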